8.1.8 Unique study identification number for each participant

Patients will be given a unique study identification number through a barcode or a QR code that will be placed into the patient paper medical record booklet. The ID identification labels will be pre-printed in bulk (specific to the district and HF) and delivered to the facilities. The patient will also be given a card with information on the study and additional barcode stickers. The sticker will be scanned using a barcode/QR code reader in the tablet each time the child presents at a HF. In the registration module on the tablet, an advanced search system will be created that uses the study identification number, the name of the child, the name of the mother or father or caregiver and the date of birth, so that the child can be identified with certainty and former consultations, if any, can be retrieved, and linked to the new consultation. The same code will also be used in order to link the laboratory results from surveillance

activities back to the child's consultation information.

8.2 Objective 2: Adapt the algorithm to epidemiological and demographic conditions

The algorithm will be improved in terms of diagnostic and prognostic accuracy and adapted to local fluctuations in epidemiology, demography, geography and resource availability. Each potential modification will first be evaluated by the Tanzanian clinical expert group for its clinical coherence, safety and potential benefit and then applied to the retrospective data. If these analyses confirm both a clinically relevant positive impact and estimate that there will be sufficient future cases during the study period to detect this improvement, the change in the algorithm will be tested in a randomized sub-study using the same study design as in Phase 1, except that randomization will take place at patient level rather than HF level. If the positive impact is confirmed in the sub-study, the modification will be implemented in all relevant locations/patient sub-groups. If the retrospective analyses confirm a positive and potentially clinically relevant impact of a modification where resource savings is also expected but there will not be sufficient power to formally test the change during the study period, the modification will be implemented and monitored based on the related outcome indicators. If the impact of the modification achieves the expected results given the accumulated data at the end of the study period, it will be retained.

During the sub-studies, HCWs attending a child who could potentially benefit from this modification in the algorithm will be informed about the potential change in the algorithm. Either the modified branch or the original branch of the algorithm will then randomly appear on the screen to guide the HCW's decisions. Antimicrobial prescriptions and clinical cure, as well as all the other available and outcome measures relevant for the algorithm change, will be assessed the same way as in Phase 1 and compared between children managed with the modified and the original version of ePOCT+. If the benefit is confirmed by the sub-study, the new algorithm branch will be implemented for all relevant children in the relevant HFs. If the benefit is not confirmed, the original version of the algorithm will be used in all involved children.

If shown to be promising according to the analyses of the retrospective data and considered feasible to implement, we will be testing modifications in the algorithm with a focus on the aims described below. Other types of modifications might also be tested if considered important by the clinical experts.

Adapting the frequency of mRDT testing to malaria prevalence:

As recommended by WHO (WHO 2011), in geographical areas where the positivity rate of malaria RDT is normally or seasonally falls below 1% (based on the data gathered through the use of ePOCT+), we will modify the "fever" branch of the algorithm to target malaria testing on the patient population at risk of having malaria. To do so, we will use the combination of demographic (e.g. village where the child lives), exposure (e.g. recent travel to an endemic area) and clinical (e.g. no other documented infection) criteria shown in the data analyses to best predict the presence of malaria. In this specific geographical area, we will thus randomize (at patient level) febrile children to be managed either using the original algorithm "fever" branch (that recommends all children to be tested for malaria), or using the modified version of the "fever" branch (that targets testing to the children at risk for malaria). If we measure that the clinical cure rate is equivalent to that of children managed with the original "fever" branch, the later will be implemented for all children in that geographical area. In case the positivity rate would later increase in that area due to resurgence of malaria, the application would revert to the original "fever" branch until malaria prevalence goes down again.

This dynamic malaria testing strategy would reduce the number of malaria tests used (that would likely have been negative) and also increase the percentage of mRDTs that are positive, which will improve the motivation and trust of HCWs in malaria testing. This strategy has already been implemented in some areas or countries in Africa using malaria predictors described in the literature, but not yet based on individual patient local data as it will be done in the present study.

Improving the accuracy of pneumonia diagnosis:

The same study design as for malaria testing will be used to improve pneumonia diagnosis accuracy using a combination of clinical predictors or new diagnostic tools, and/or to save CRP rapid tests in children with cough or difficult breathing. The new “cough” branch of the algorithm will be implemented in all children either if the clinical cure rate with the new branch is expected to be better than that of children managed with the original “cough” branch OR if the number of CRP tests used is expected to decrease.

Assessing the utility of dengue rapid tests in outbreak conditions:

If the microbiological surveillance in a few sentinel sites (see chapter 8.3) identifies a dengue outbreak, a dengue rapid test will be added to the “unspecific fever” branch of the algorithm and tested using the same study design as above. The modified “unspecific fever” branch including dengue testing will be implemented in all children if the clinical cure rate with this new branch is better (i.e. >30% decrease in the clinical failure rate) than that of children managed with the original “unspecific fever” branch. As soon as the dengue outbreak is over, the “unspecific fever” branch will revert to the original version and the use of dengue rapid tests will be stopped.

Assessing the utility of typhoid rapid tests in high prevalence conditions:

If the prevalence of typhoid in febrile children is shown to be >10% in a certain area or time period (based on the microbiological surveillance data), using rapid tests, even with sub-optimal sensitivity and specificity as it is the case for now, could be beneficial from a clinical point of view. Indeed, with a pre-test probability of 10% and a positive likelihood ratio of 4 for the typhoid RDT, the post-test probability is 30%. The performance of the test can be enhanced by adding clinical predictors identified in previous studies in Tanzania (De Santis et al. 2017).

In this situation, a typhoid rapid test will be added to the “unspecific fever” branch of the algorithm and its clinical utility assessed using the same design as above. The new “unspecific fever” branch including the typhoid rapid test would be implemented in all children of the high prevalence area, if the clinical cure rate with the new branch is better (i.e. >30% decrease in the clinical failure rate) than that of the original branch. When typhoid prevalence decreases, the “unspecific fever” branch will revert to its original version.

Improving prediction of a severe clinical outcome:

If a combination of demographic, clinical and/or laboratory predictors, or a new POC test, seems to allow for better identification of children who will develop severe disease and thus be hospitalized secondarily or die, the benefit of adding an alert to HCWs in the algorithm, recommending them to refer the child to hospital, will be evaluated. If adding this alert allows to decrease mortality by at least 10%, it will be implemented for all children.

Adapting the algorithm to improve cure rates of children with chronic disease risk factors:

If specific predictors of clinical failure can be identified in children with chronic disease risk factors (e.g. malnourished, HIV positive children, children with sickle cell disease), the relevant branches of the algorithm will be modified for these children (e.g. an antibiotic treatment may be recommended in a child with a certain clinical constellation). This personalized algorithm will be implemented in all children with the chronic disease risk factor if there is a clinical benefit as described above.

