|--|--|

| | |
|------------------------------------|---|
| | 
 - Carbon footprint of the intervention or carbon-saving due to the intervention |
| Procedures and measurements | 
Objective 1: Improve the integrated management of sick children
 
In Phase 1, in each region, after a pilot period of 6 months to test all the e-tools, eligible HFs will be randomized (by Region and HF) to the intervention or control arm. Sick children will be enrolled over a period of 6 to 9 months.
 
Primary outcome measures: (i) For assessing clinical cure at Day 7, a simple questionnaire (asking if the child is still sick, was hospitalized secondarily, or died) will be administered to all caregivers by phone; (ii) For measuring antibiotics prescribed at initial consultation, the treatment data recorded in the tablets or PCs by HCWs throughout the study will be compared between intervention and control arms.
 
Secondary outcome measures: To determine the quality of the consultation made by CHWs, including the rational use of antimicrobials (antibiotics and antimalarials), two sources of data will be used and compared between intervention and control arms:
 
 - the final decision on referral, tests performed, final diagnoses retained and treatment prescribed will be recorded in the tablets or PCs by HCWs at initial consultations and re-attendance visits. - during a cross-sectional survey, observers in the consultation room will record key symptoms and signs assessed by HCWs, diagnostic tests requested, final decision on referral, final diagnoses retained and treatment prescribed. 
Control arm: In control PHC facilities, sick children will be assessed, diagnosed and treated as per routine protocols by clinicians. A similar but simplified tablet or PC application will also be used in control facilities, but only to record outcome measure related data using an electronic case report form. HCWs in control facilities will be offered the usual training and supervision proposed by the CHMT.
 
In Phase 2, all selected HFs in the two regions will receive the intervention. Indicators monitored over time and across geographical areas will be measured the same way as in Phase 1, except that clinical cure, secondary hospitalizations and deaths may or may not be assessed through a phone call or an automated SMS or call to caregivers using the same simple questionnaire.
 
Objective 2: Improve the algorithm and adapt it to spatiotemporal variations
 
The algorithm will be improved in terms of diagnostic and prognostic accuracy and adapted to local fluctuations in epidemiology, demography, geography and resource availability. These modifications will be designed and supervised by clinical experts, based on accumulated data captured during the study in real-time and analyzed, including by ML when necessary. All modifications will first be tested on retrospectively collected data. If these analyses confirm an expected positive impact, the change in the algorithm will be implemented and its impact will be monitored through the continuous analysis of data looking at the related outcome indicators. For major modifications in the algorithm, a formal randomized sub-study will be conducted to assess precisely the potential benefit (or harm) on clinical outcome or non-inferiority. HCWs attending a child who could potentially benefit from this modification will be informed about the change in the algorithm. Either the modified branch or the standard branch of the algorithm will then appear on the screen to guide the HCW's decisions. Antimicrobial prescriptions, clinical cure and other outcomes related to the expected impact will be assessed the same way as in Phase 1 and compared between children managed with the new and the standard version of ePOCT+. If the positive impact is confirmed by the sub-study, the new algorithm branch will be implemented for all relevant children in the relevant HFs. Minor modifications in the algorithm (e.g. adding a non-critical symptom such as myalgia, or a slight modification of threshold of a laboratory test) will be implemented without sub-study, but some outcome indicators may be monitored.
 
Objective 3: Enhance disease surveillance and outbreak detection
 
All data generated by ePOCT+ will be sent to a central sever based at IHI. Data will be visualized through the medAL-outbreak dashboard made available to district health authorities using the key indicators they will have chosen. To enhance disease
 |

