The ePOCT+ tool will be extended to the 20 HFs serving as controls in Phase 1, as well as up to 60 additional neighboring facilities of our target area, to reach a total of up to 100 facilities (around 60 in Morogoro and 40 in Mbeya). In Phase 2, an adaptive study design will be used measuring the same outcome indicators as in Phase 1. The medical content of the algorithm will no longer be static, but rather modifiable according to the local data captured by ePOCT+ during Phase 1. Each modification will be designed and evaluated by the clinical expert group for its coherence, safety and potential benefit. Modifications in the algorithms designed to perform as well as the original algorithm but using fewer/different resources will be implemented in the facilities they were designed to serve (for example, if certain facilities do not have access to a certain resource). Similarly, modifications designed to personalize the algorithm according to demographic characteristics, geography or season will be implemented on the target population for which they were intended. Modifications of ePOCT+ aimed at improving health outcomes of subgroups of patients (for example those with respiratory infections) will be implemented in a sub-study where patients are randomized at an individual level. Modifications confirmed as safe and useful will then be implemented, while the non-beneficial changes will not be retained.

Examples of algorithm modifications expected to have positive impacts that will be explored for implementation are: 1) adapting the frequency of malaria testing in areas with very low endemicity; 2) improving the accuracy of pneumonia diagnosis, including , including through the use of novel POC diagnostic tools; 3) assessing the utility of using dengue rapid tests if an outbreak occurs; 4) or typhoid rapid tests in areas of high prevalence; 5) improving the prediction of severe disease; 6) improving the algorithm for malnourished or HIV positive children and; 7) testing sick children for sickle cell disease.

Figure 5: Study design overview.

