Positive impact modification is defined as a change in the algorithm expected to increase the clinical cure rate and/or decrease resources needed* and/or to have another positive clinical or health system related impact.

* Resources needed include but are not limited to medicines prescribed, diagnostic tests ordered by HCWs, or time spent to perform a consultation.

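### The Phase 2 adoption rule for the new cough branch can be met by an expected fall in CRP tests alone, with no condition on clinical cure

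*Protocol*

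**What the plan says.** The pneumonia aim in Protocol 8.2 has two parts. The first sets the design: "The same study design as for malaria testing will be used to improve pneumonia diagnosis accuracy", with saving CRP tests named as a possible goal. The second sets the adoption rule. The new branch is given to all children if its cure rate is expected to exceed that of the original branch, "OR if the number of CRP tests used is expected to decrease".

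Other text bears on this rule:

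- **Protocol 8.2, general rule.** Experts first review each modification for coherence, safety and benefit. Sub-studies compare antimicrobial prescription and cure between branches. Then: "If the positive impact is confirmed in the sub-study, the modification will be implemented in all relevant locations/patient sub-groups". And: "If the benefit is not confirmed, the original version of the algorithm will be used in all involved children".
- **Protocol 8.2, underpowered changes.** A promising change that should also save resources, but cannot be formally tested in the time left, is implemented, monitored and kept if it performs as expected.
- **Protocol 8.2, malaria testing.** "If we measure that the clinical cure rate is equivalent to that of children managed with the original" fever branch, the change is adopted.
- **Protocol 7.2.** A positive impact modification is one "expected to increase the clinical cure rate and/or decrease resources needed", or one with another positive clinical or health-system effect.
- **Synopsis, Procedures and measurements, Objective 2.** For major modifications a sub-study assesses "the potential benefit (or harm) on clinical outcome or non-inferiority".
- **Protocol 3.2.** Changes "designed to perform as well as the original algorithm but using fewer/different resources will be implemented in the facilities they were designed to serve". Modifications shown to be safe and useful are implemented; the others are not kept.
- **Protocol 10.1 and 10.1.2.** Section 10.1 defines non-inferiority in cure (a 30% limit on failures) and resource superiority (a decrease of at least 25%). Section 10.1.2 leaves the acceptable difference to each sub-study and takes the larger of the clinical and resource sample sizes.

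**The concern.** The rule written for this branch joins a clinical criterion and a resource criterion by OR, so the resource criterion suffices alone. It sets no cure condition, no minimum saving and no test. Both limbs speak of what is expected, whereas the general rule of the section speaks of what a sub-study confirms.

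Protocol Table 2 gives the purpose of CRP in children with respiratory symptoms as better targeting of antibiotics. A branch that uses fewer CRP tests could therefore change who is treated, and so change cure. If cure fell while CRP use also fell, the adoption sentence would be satisfied. A team relying on the general text might well decline to adopt the branch, but it would be choosing between conflicting passages, possibly with the results in hand.

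**Working it through.** The plan gives no figure for this rule, so the main check is textual.

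**1. The comparable aim.** Malaria testing and the cough branch are the two aims in 8.2 that may save tests, and the second borrows the first's design.

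| | Malaria testing | Cough branch, CRP limb |
|---|---|---|
| Resource aim | fewer malaria tests | fewer CRP tests |
| Clinical condition for adoption | equivalent cure | none |
| Evidence word | measured | expected |

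The dengue, typhoid, severe-outcome and chronic-risk aims also carry clinical criteria. They set out to improve outcomes, so they say less about how a test-saving change should be judged. Phase 1 is a further comparison: the antibiotic test is conditional on non-inferior cure (Protocol 10.1.1 and 10.3).

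**2. Does the general rule of 8.2 supply the missing condition?** It adopts a change once positive impact is confirmed. Protocol 7.2 defines a positive impact modification with and/or, so a resource saving qualifies alone. A confirmed CRP saving can thus satisfy the general rule without any finding on cure.

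**3. Does other text supply it?** The Synopsis names non-inferiority only for major modifications, and the documents do not say whether a CRP-saving cough branch is major. Protocol 3.2 treats equal performance as a design intention for resource-saving changes. Its safe-and-useful sentence directly follows the one on outcome-improving sub-studies and gives no criterion for safe. Protocol 10.1 defines non-inferiority and the 25% saving, but the cough rule cites neither.

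**4. Scale of what the rule would pass over.** Failure rates of 3%, 5% and 10% are assumed. Extra failures per 10,000 children = 10,000 × p × (RR − 1).
- RR 1.15: 45, 75 and 150.
- RR 1.3 (the Phase 1 margin): 90, 150 and 300.

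**5. Cost of adding a cure condition.** Take the example in Protocol 10.1.2, cure rising from 90% to 93% (failures 10% to 7%). Assume individual randomisation, one-sided 0.025 and 80% power, so (1.960 + 0.842)² ≈ 7.849.
- Superiority size: 7.849 × (0.10×0.90 + 0.07×0.93)/0.03² = 1,353 per arm.
- Non-inferiority size, true RR 1, margin RR 1.3, log risk-ratio scale: 7.849 × 2 × (0.90/0.10)/(ln 1.3)² = 2,053 per arm. 2,053/1,353 = 1.52.
- Same margin as a risk difference (0.3 × 10% = 3 points): 7.849 × 2 × 0.10×0.90/0.03² = 1,570 per arm. 1,570/1,353 = 1.16.
- Non-inferiority power at 1,353 per arm: Φ(0.2624/√(18/1,353) − 1.960) = 0.62 on the log scale; Φ(0.03/√(0.18/1,353) − 1.960) = 0.74 on the difference scale.

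**6. If the size is already set for non-inferiority (2,053 per arm).** Assume a true 25% fall in CRP use, and cure and CRP use independent.
- CRP use 30%: CRP power Φ(0.075/√(0.3844/2,053) − 1.960) ≈ 1.00; joint power 0.80 × 1.00 = 0.80.
- CRP use 10%: CRP power Φ(0.025/√(0.1594/2,053) − 1.960) = 0.81; joint power 0.80 × 0.81 = 0.65. About 2,700 per arm brings this to 0.81.

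**The case against.** The strongest reply is that the general rule heads the section and governs its examples. That rule includes expert safety review, comparison of cure in every sub-study and return to the original branch if benefit is not confirmed. Protocol 3.2 asks for safety as well as usefulness, the Objective 2 indicators count modifications confirmed safe and useful by sub-studies, and Protocol 12.3 allows termination on evidence of harm. The wording about expectation also has a counterpart, since both the Synopsis and 8.2 let some changes go ahead and be monitored without a sub-study.

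Much of this stands. A reader might infer that the protocol has no clinical safeguard for resource-saving changes, or that the cough rule has no connection with the general rule of 8.2. The documents support neither: cure is compared in sub-studies, and several passages keep safety in view. The underpowered route also means that adoption cannot always rest on a sub-study result.

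It does not remove the conflict. Expert review comes before the data and is not a rule for acting on results. Comparing cure does not say what an unfavourable comparison does to a decision that the specific rule already allows. The definition in 7.2 stops the general rule from closing the gap.

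It is also fair that Protocol 10.1.2 deliberately leaves acceptable differences to each sub-study. That leaves the margin open; it does not say that no margin is needed.

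**Conclusion.** The point holds as a conflict between one specific adoption rule and the general text around it. As written, a CRP-saving cough branch with worse cure could meet the rule, and no other passage clearly overrides it. Whether such a branch would be adopted in practice cannot be told from the documents; the aims are themselves conditional on promising retrospective data.

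The textual finding rests on no assumed number. The illustrative harm (45 to 300 extra failures per 10,000) and the costs rest on assumed failure rates, CRP use and effects, because the documents give none for children with cough. The 16% to 52% range reflects the choice of analysis scale, which the protocol does not fix for sub-studies. The point should be resolved before a cough sub-study starts; it does not affect Phase 1.

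**What to change.** Reconcile the pneumonia rule in Protocol 8.2 with the general and malaria rules of that section, the Objective 2 procedures in the Synopsis, and Protocol 3.2, 7.2 and 10.1. In particular:

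- Where a sub-study is run, base adoption under either limb on its result.
- Make the resource limb conditional on non-inferior cure as well as the CRP decrease. Fix the margin and its scale before the sub-study starts, as Protocol 10.1.2 allows, and say how the 25% definition in 10.1 applies.
- Where the underpowered route applies, state that retention depends on monitored cure as well as CRP use.

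**Cost.** The text change is a sentence or two in 8.2 and a line in each sub-study plan. A joint requirement lowers the chance of adoption somewhat. If the sub-study is sized for non-inferiority, no children are added at CRP use of about 30% or more. At 10% failure and 10% CRP use, about 2,700 rather than 2,053 per arm (32% more) would be needed. If it is sized only for superiority in cure, the increase for 80% non-inferiority power is 16% to 52%.

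Sub-studies already plan day-7 follow-up. The underpowered route may not have it: Protocol 8.1.7 limits Phase 2 follow-up contact to sub-study children, while 7.1 lists day-7 cure as an indicator for all facilities. Those two passages need to agree before cure can be monitored there.
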